3.2.4 Monitoring of RAD001 suspected toxicities

Patients whose treatment is interrupted or permanently discontinued due to an adverse event or abnormal laboratory value suspected to be related to RAD001 must be followed at least weekly until the adverse event or abnormal laboratory resolves or returns to grade 1. If a patient requires a dose delay of > 21 days from the intended day of the next scheduled dose, then the patient must be discontinued from the study.

3.2.5 Known Side Effects of RAD001

Adverse events most frequently observed with RAD001 are rash, stomatitis/oral mucositis, fatigue, headache, anorexia, nausea, vomiting, diarrhea. Infections have not been notably frequent or severe. Non-infectious pneumonitis has also been observed. The majority of these AEs have been of mild to moderate severity (CTC grade 1-2). Overall, the most frequently observed laboratory abnormalities include reduced blood counts, hyperlipidemia mostly reported as hypercholesterolemia and/or hypertriglyceridemia.

3.2.5a The principal DLT in Phase 1 trials has been Grade 3 stomatitis. For guidance on management of stomatitis refer to Section 3.2.6.1

3.2.5b Hyperlipidemia was reported as a serious adverse reaction. It is a recognized side-effect of rapamycins. Use of lipid-lowering drugs should be associated with dietary recommendations. Monitoring of blood lipid levels requires patients to be fasting so that this aspect must be verified when interpreting results. For guidance on management of hyperlipidemia refer to Section 3.2.6.2.

3.2.5c Hyperglycemia was reported as a serious adverse reaction. Similarly, the fasting state of patients should be verified when interpreting results. For guidance on management of hyperglycemia refer to Section 3.2.6.2.

3.2.5d Pneumonitis is a recognized adverse effect of rapamycins (sirolimus, temsirolimus, and everolimus). Numerous case reports in the literature suggest that rapamycin-associated pneumonitis is relatively unaggressive, limited in extent, and reversible upon drug discontinuation. The term 'pneumonitis' is used here to describe non-infectious, non-malignant infiltration in the lungs which is evident radiologically. More precise diagnosis should follow histocytological examination following lung biopsy, generally during bronchoscopy which may or may not be symptomatic. Advice on the management of pneumonitis has been provided in Table 3-2a.

In oncology studies with RAD001, severe pneumonitis suspected as drug-related has been reported as a serious adverse event on 13 occasions and additionally in the following associated preferred terms including acute respiratory distress syndrome (n=2), alveolitis (n=1) and allergic alveolitis (n=1), interstitial lung disease (n=10), lung infiltration (n=23), cryptogenic organizing pneumonia, lung consolidation, pulmonary alveolar haemorrhage, pulmonary toxicity and pulmonary fibrosis (n=1, each). One fatal case of drug-related

pneumonitis was reported for a patient with metastatic infiltrating ductal carcinoma of the breast treated with 10 mg/day, which developed approximately two months after starting RAD001. Cytology for both the pleural and pericardial fluids were positive for malignancy. The death was considered possibly related to the underlying late stage tumor and study drug. Additionally, one patient treated with 10 mg/day died due to severe acute respiratory distress syndrome and septic shock. Thoracic CT scan demonstrated condensation in the majority of the left lower lobe and frosted glass appearance in the left upper lobe, lingula, and right lung.

Along with the cases of non-infectious pneumonitis, serious opportunistic infections have also been reported in cancer patients treated with RAD001: mycobacterium, aspergillus, and fatal candidal sepsis, and fatal pneumocystis carinii in particular. Because RAD001, as other rapamycins, inhibits proliferation of activated lymphocytes and reduces neutrophil counts, treatment with RAD001 must be considered as predisposing patients to the risk of infection. This risk will be higher in patients severely immunocompromised because of their underlying disease and/or co-medications. Outcome may be fatal in case of serious infections.

3.2.5e Pericardial effusions, pleural effusions, and weight loss have been reported as serious adverse events with suspected causality. Due to the imprecision of causality assessments it should not be assumed that all of these events are indeed the result of therapy with everolimus since confounding factors are present relating mainly to complications of the underlying disease and to the use of concomitant medications.

3.2.5f A reduction in blood cell counts is frequent when RAD001 therapy is initiated. Without clinical significance and infrequently, anemia and thrombocytopenia have been reported. In heavily pretreated patients with aggressive lymphoma, the incidence of grade 3 anemia, neutropenia, and thrombocytopenia was reported to be 11%, 16%, and 30%, respectively. Serious, suspected drug-related hemorrhages have been exceptional. Nevertheless, RAD001 should be considered as predisposing patients to hemorrhage, potentially fatal, should they develop severe drug-related thrombocytopenia.

3.2.5g Discrete, reversible changes in liver enzymes have been found to occur in numerous patients during treatment with RAD001 in oncology clinical studies, and in a study in rheumatoid arthritis. In oncology studies, these changes may be evident only in patients without severe underlying morbidity. The increase in transaminase's (AST and ALT) generally appears after 4 weeks of treatment. In all but a few cases it does not exceed Grade 1 ($\leq 2.5 \times \text{ULN}$). Similarly, mild increases in alkaline phosphatases can coexist. Spontaneous corrections or intermittent correction with continued treatment can occur. Serum bilirubin is not increased. In studies of patients with advanced cancers, clinically relevant changes in liver enzymes have been invariably associated with the presence of liver metastases and/or progression of the underlying cancer.

3.2.5h Renal failure has been reported in five suspected cases to date. One patient with no alternative explanation made a complete recovery following study drug adjustment and no treatment/therapy for the event. The rest of the patients had concurrent morbidities, which might have contributed to the reported events.

3.2.5i Hypophosphatemia, hypomagnesemia, hyponatremia and hypocalcemia have been reported as serious adverse reactions. Electrolytes should be monitored in patients treated with RAD001.

Table 3-1 provides general recommendations for the management of patients, with suspected drug toxicities while on treatment with RAD001 as single-agent therapy.

More detailed information regarding RAD001 reported suspected toxicities and individual cases is provided in the [Investigator's Brochure].

3.2.5j Reactivation of Hepatitis B (HBV) has been observed in sporadic cases with patients in this setting with everolimus. Use of antivirals during anti-cancer therapy has been shown to reduce the risk of Hepatitis B virus reactivation and associated morbidity and mortality. A detailed assessment of Hepatitis B/C medical history and risk factors must be done for all patients at screening, with testing performed prior to the first dose of everolimus.

Patients who test positive for a past or active Hepatitis B infection should be given prophylactic administration. If the patient has a positive Hepatitis B test result, they should be treated with Hepatitis B anti-viral lamivudine 100 mg prior to start of RAD001 therapy and throughout the treatment period with RAD001. Some associated toxicities to the lamivudine may include headache, diarrhea, and rash. If the patient needs to be treated with lamivudine, the cost of the treatment will be charged to the patient's insurance. For guidance on management of Hepatitis B and C reactivation, refer to Section 3.2.6.4.

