3.2.3 Interruption or discontinuation of treatment

For patients who are unable to tolerate the protocol-specified dosing schedule, dose adjustments are permitted in order to keep the patient on study drug. Patients may be re-escalated back to the previous dose if he/she is stable, his/her symptoms are related to disease and not treatment, and you receive the PI's permission. If administration of RAD001 must be interrupted because of unacceptable toxicity, drug dosing will be interrupted or modified according to rules described in Table 3-1. Toxicity will be assessed using the NIH-NCI Common Terminology Criteria for Adverse Events, version 3.0 (CTCAEv3.0, (<http://ctep.cancer.gov/forms/CTCAEv3.pdf>)).

Table 3.0 RAD001 dose level modification guidelines

Dose level	Dose and schedule
0 (starting dose)	10 mg po daily
-1	5 mg po daily
-2	5 mg po every other day

If patients are unable to tolerate dose level -2, the patient will come off study.

Table 3-1 Criteria for dose-modification in case of suspected RAD001 toxicity and re-initiation of RAD001 treatment

Toxicity	Actions
Non-hematological toxicity	
Grade 2 (except pneumonitis – refer to Table 3-2a)	If the toxicity is tolerable to the patient, maintain the same dose. If the toxicity is intolerable to patient, interrupt RAD001 until recovery to grade ≤ 1 . Then reintroduce RAD001 at same dose. If event returns to grade 2, then interrupt RAD001 until recovery to grade ≤ 1 . Then reintroduce RAD001 at the lower dose level.
Grade 3 (except hyperlipidemia*) (except pneumonitis – refer to Table 3-2a)	Interrupt RAD001 until recovery to grade ≤ 1 . Then reintroduce RAD001 at the lower dose level. For pneumonitis consider the use of a short course of corticosteroids.
Grade 4 (except hyperlipidemia*)	Discontinue RAD001.
Hematological toxicity	
Grade 2 Thrombocytopenia (platelets $<75, \geq 50 \times 10^9/L$)	Interrupt RAD001 until recovery to grade ≤ 1 ($>75 \times 10^9/L$). Then reintroduce RAD001 at initial dose. If thrombocytopenia again returns to grade 2, interrupt RAD001 until recovery to grade ≤ 1 . Then reintroduce RAD001 at the lower dose level.
Grade 3 Thrombocytopenia (platelets $<50, \geq 25 \times 10^9/L$)	Interrupt RAD001 until recovery to grade ≤ 1 (platelets $\geq 75 \times 10^9/L$). Then resume RAD001 at one dose level lower. If grade 3 thrombocytopenia recurs, discontinue RAD001.
Grade 4 Thrombocytopenia (platelets $< 25 \times 10^9/L$)	Discontinue RAD001.

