3.4 Visit schedule and assessments

3.4.1 Visit schedule

The visit schedule is outlined in Table 3.4a below.

General/safety assessments	Study entry (within 14 days of day 1 unless otherwise noted))	Day1 ²	At office visit every 4 weeks ¹	Every 8 weeks for max. 24 months ¹
Informed consent	X (within 28 days of day1)			
Medical history, height and vital signs	X		X	
Inclusion/exclusion criteria	X			
ECOG Performance status	X	X	X	
QOL questionnaire (EQ-5D)		X	X	
MTC-related symptoms questionnaire (MTC subjects only)		X	X	
Physical examination and weight	X	X	X	
ECG	X			
AE's and con-medications/treatments	X	X	X	
Laboratory assessments				
Pregnancy test for WOCBP (female subjects <50)	X			
Coagulation tests	X			
Hepatitis B tests (Hep B Core, Hep B Surf AB, Hep B Surf AG, HBV DNA) ³	X (within 30 days of Day 1)		X (only HBV DNA if positive at baseline)	
Hepatitis C test (HCV RNA PCR) ³	X (within 30 days of Day 1)			
Hematology and blood chemistry	X		X	
Urinalysis	X			
Calcitonin and CEA if elevated at baseline (only MTC subjects)	X		X (if elevated at baseline)	
Thyroglobulin and anti-thyroglobulin antibodies (only DTC subjects)	X		X (if elevated at baseline) ⁴	
Free T4 and TSH	X		X	
Radiological assessments				
CT/MRI neck, chest, abdomen ⁵	X (within 30 days of day 1)			X
Whole body bone scan (only MTC, FTC, HCTC subjects)	X (within 30 days of day 1)			
First dose of Rad001		X ²		
Rad001 dispensed/returned				X

- ¹+/- one week depending on appointment availability due to holidays or unforeseen events
- ²First dose of RAD001 may start the morning of Study Day 2.

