3.4.1.2 Treatment period procedures

The first does of RAD001 may be administered on the same day as enrollment but no more than 10 business days after enrollment. The treatment period begins on the first day of treatment with RAD001. The time points of study visits are outlined in table 3.4a.

If a subject is unable to come into the clinic for a required study visit or if unforeseen events occur, the visit procedures may be performed within a one week time frame.

The following assessments will be performed at each clinic visit according to table 3.4a throughout the treatment period:

Physical examination,

ECOG performance status,

blood pressure, respiratory rate, resting pulse, temperature, and weight.

Patient reported outcomes questionnaire (EQ-5D), see appendix

Medullary thyroid cancer-related symptoms questionnaire, see appendix

Laboratory evaluations are done at screening and monthly and need not be repeated on day 1.

CT scans (contrast-enhanced or MRI scan (contrast-enhanced or PET CT scans of areas with known disease and that are of acceptable quality every 8 weeks with a 5 business-day time window in case unforeseen events occur. Evaluation according to RECIST criteria compared to previous scan.

Documentation of all adverse events will occur at each clinic visit and at any other time point when necessary.

Survival status will be recorded for all patients until death or 5 years from study entry

Subjects who complete 24 months of therapy without progression may continue treatment with RAD001 and will have the following assessed:

- Physical exam and labs at the discretion of the physician approximately every 4-6 weeks. Deviation from this schedule must first be approved by the Principal Investigator.
- Disease Status per RECIST approximately every 3 months
- Serious Adverse Events (SAEs) per section 3.4.3.2
- Drug accountability

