3.4.1.3 End of treatment period procedures

Patients removed from study treatment for reasons other than progression of disease should continue to be followed for first disease progression per RECIST. See footnote #5 in 3.4.1 for details.

All patients who terminate treatment with RAD001 should be evaluated in the outpatient clinic within 5 business days after the last dose of RAD001 and again 4 weeks after their last dose of RAD001 (plus or minus one week depending on appointment availability due to holidays or unforeseen events). In certain instances, if a patient is unable to return to clinic every effort should be made to follow-up with a phone call to the patient or their provider.

This evaluation will include:

Physical examination,

ECOG performance status,

blood pressure, respiratory rate, resting pulse, temperature, and weight.

Patient reported outcomes questionnaire (EQ-5D), see appendix

Medullary thyroid cancer-related symptoms questionnaire, see appendix

Laboratory evaluations are also performed according to table 3.4a. The necessary components of the laboratory tests are outlined below. Documentation of all adverse events

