3.4.1.4 Study procedures

3.4.1.4.1 Laboratory evaluations

Hematology

Hematology must include hemoglobin, hematocrit, platelets, total white blood cell count (WBC) and differential. PT (INR) evaluation will be included for baseline evaluations.

ANC will be determined by this equation:

$$(\% \text{Neutrophils} + \% \text{Bands}) (\text{WBC Count} \times 10^1) = \text{ANC}^1$$

Blood chemistry

Blood chemistry must include sodium, potassium, chloride, bicarbonate, calcium, glucose, creatinine, blood urea nitrogen, albumin, total protein, SGOT (AST), SGPT (ALT), total bilirubin, alkaline phosphatase, uric acid, phosphorus, serum lipid profile (triglycerides, total cholesterol, HDL and LDL).

¹ WBC Count is in K/UL units.

Because accurate serum glucose and lipid measurements are required, patients should be fasting at the time of the blood sampling.

Tumor markers which were elevated prior to treatment start with RAD001 will be assessed every month or whenever clinically indicated. Patients with differentiated thyroid cancer will have thyroglobulin and thyroglobulin antibody measured every month and patients with medullary thyroid cancer will have CEA and calcitonin levels evaluated every month (see table 3.4a)

The Hepatitis B and C screening tests (Hep B Core, Hep B Surface antibody, Hep B Surface antigen, HCV RNA-PCR) need to be performed at baseline. HBV DNA follow-up testing should be done according to table 3.4a and section 3.2.6 “Management of Hepatitis B or C Reactivation,” depending on results from baseline.

Urinalysis

Standard urinalysis assessment (pH, protein, glucose, blood, ketones, and leukocytes) should be performed at baseline. This must be supplemented with laboratory quantification of any potentially relevant abnormalities.

Vital signs

Vital sign assessment consists of height (first visit), pulse, blood pressure, respiration rate, temperature and weight. Blood pressure, pulse and respiration rate should be measured on patients after at least 3 minutes in the sitting position.

Physical examination

Physical examination will be performed monthly and must comprise a total body examination. Significant findings made after the start of study drug which meet the definition of an Adverse Event must be recorded.

ECG

A standard 12 lead ECG is to be performed during screening and significant findings must be recorded.

Performance status

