5.7 Participant Registration and Randomization

To register a participant, the following documents should be completed by the DF/HCC Multi-Center Protocol participating site and faxed to or e-mailed to the research manager at the Lead Institution:

- Copy of required laboratory tests (coagulation test, hematology and blood chemistry, urinalysis, free T4, TSH, calcitonin/CEA (only MTC subjects), thyroglobulin/anti-thyroglobulin antibodies (only DTC subjects), and pregnancy test)
- Signed informed consent form
- HIPAA authorization form (if separate from the informed consent document)
- Other appropriate forms (e.g., Eligibility Screening Worksheet/Registration form, source documents confirming eligibility (pathology reports, radiology reports showing progression within 6 months per RECIST criteria, treatment summary forms))

The research DF/HCC Multi-center Protocol participating site will then call or e-mail the Lead Institution or designee to verify eligibility. To complete the registration process, the Lead Institution or designee will:

- Verify the patient meets all eligibility criteria through source documentation provided by external site.
- Register the participant on the study with the DF/HCC Quality Assurance Office for Clinical Trials (QACT).
- Fax or e-mail the participant case number, and if applicable the dose treatment level, to the participating site
- Call the research nurse or data manager at the participating site and verbally confirm registration.

Please fax all registrations to the research manager, [name], at the Lead Institution. The fax number is [contact]. If you have any questions, please call [contact].

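### Magnesium is missing from the mandatory chemistry list, although Section 3.2.5i names hypomagnesemia as a reported serious reaction and asks for electrolyte monitoring

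*Combined protocol and SAP*

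**What the plan says.** Section 3.2.5i (Known Side Effects of RAD001) reads: "Hypophosphatemia, hypomagnesemia, hyponatremia and hypocalcemia have been reported as serious adverse reactions. Electrolytes should be monitored in patients treated with RAD001". It does not say which electrolytes to measure or how often.

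The analytes are set in Section 3.4.1.4.1. The list opens "Blood chemistry must include sodium, potassium, chloride, bicarbonate, calcium, glucose, creatinine, blood urea nitrogen, albumin, total protein", continues with AST and ALT, and ends "total bilirubin, alkaline phosphatase, uric acid, phosphorus, serum lipid profile (triglycerides, total cholesterol, HDL and LDL".

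The timing is set in Table 3.4a, where the row "Hematology and blood chemistry" is marked at study entry and at the 4-weekly visits. Section 3.4.1.2 adds: "Laboratory evaluations are done at screening and monthly and need not be repeated on day 1". For the end of treatment, Section 3.4.1.3 says: "Laboratory evaluations are also performed according to table 3.4a". Appendix D, Section 5.7, asks sites registering a participant for a "Copy of required laboratory tests (coagulation test, hematology and blood chemistry, urinalysis, free T4, TSH" and further items specific to the tumor type, plus a pregnancy test.

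**The concern.** The protocol identifies four electrolyte disorders as serious reactions to the study drug and asks for monitoring, but its operative laboratory list carries through only three. Sites order tests from the list and the visit table, not from the side-effect narrative. Under Appendix D, Section 9.3, site compliance is checked against Section 3.4, so a site that never measures magnesium would still pass.

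Three things are at stake:

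- **Detection.** Asymptomatic low magnesium would go unseen.
- **Dosing.** Table 3-1 ("Criteria for dose-modification in case of suspected RAD001 toxicity and re-initiation of RAD001 treatment") works by toxicity grade. A disorder graded on a laboratory value cannot trigger it when no value exists.
- **Interpretation.** Without a screening value, a low result found later cannot readily be judged new or worsened, which is what the adverse event definition in Section 3.4.3.1 turns on. If some sites test and others do not, an absence of reported hypomagnesemia says little.

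**Working it through.** No sample size, power or error rate is involved. The check compares the four disorders named in Section 3.2.5i with the required list, and then looks for magnesium elsewhere.

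**Size of the mandatory list (Section 3.4.1.4.1)**

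- Sodium, potassium, chloride, bicarbonate, calcium, glucose, creatinine, blood urea nitrogen, albumin, total protein: 10
- AST, ALT: 2
- Total bilirubin, alkaline phosphatase, uric acid, phosphorus: 4
- Triglycerides, total cholesterol, HDL, LDL: 4

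Total: 10 + 2 + 4 + 4 = 20 analytes. Magnesium is not among them.

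**Match to Section 3.2.5i**

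| Disorder named in 3.2.5i | Analyte needed | On the mandatory list? |
|---|---|---|
| Hypophosphatemia | Phosphorus | Yes |
| Hypomagnesemia | Magnesium | No |
| Hyponatremia | Sodium | Yes |
| Hypocalcemia | Calcium | Yes |

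Coverage is 3 of 4.

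**Other places where magnesium could have been added**

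- Table 3.4a: one general hematology and chemistry row, and no separate magnesium row.
- Section 3.4.1.3: refers back to Table 3.4a.
- Section 3.4.1.4.1, special tests: none specified; left to a possible future amendment.
- Section 3.4.3: refers to blood chemistry in general.
- Appendix D, Section 5.7: the same.

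In the supplied text, magnesium appears only within the word hypomagnesemia in Section 3.2.5i.

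**Comparison with the other laboratory-detectable risks in Section 3.2.5**

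Each of the others has a test in the plan: lipids and glucose (3.2.5b, c), blood counts (f), liver enzymes and bilirubin (g), creatinine and urea nitrogen (h), and hepatitis B DNA (j). Magnesium is the exception, and no reason is given, which suggests an oversight rather than a choice.

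**Which values would change dosing**

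For non-hematological toxicity, Table 3-1 has no rule at grade 1. It keeps the dose at a tolerable grade 2, interrupts at an intolerable grade 2 or at grade 3, and discontinues at grade 4. For a patient without symptoms, therefore, only a grade 3 or 4 value suspected to be due to RAD001 would normally alter treatment.

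**The case against.** The strongest reply is that the two sections do not conflict. The chemistry list is a minimum, Section 3.2.5i is current protocol text, and a site can satisfy both by ordering magnesium. The harm needs a site that follows the list and overlooks the narrative. This is correct as far as it goes, but Section 3.2.5i gives neither analytes nor a schedule, and compliance is checked against Section 3.4. The gap is one of drafting, and it can still lead to magnesium not being measured.

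A second reply is that the impact is small and unquantified. The documents give no incidence, electrolyte disorders are not among the most frequent laboratory abnormalities in Section 3.2.5, and the Investigator's Brochure, which holds the detail, was not available for this review. Section 3.4.3.1 counts a laboratory abnormality as an adverse event only if it produces signs or symptoms, is clinically significant or needs therapy. Examinations and adverse event review every 4 weeks, and at least quarterly review by the monitoring committee, should pick up symptomatic cases. All of this stands and limits the importance of the point. It does not supply a measurement for silent cases, and judging clinical significance or need for therapy without symptoms requires one.

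A third reply is that the dose rules are engaged only at grade 3 or 4 in asymptomatic patients, and that laboratory tests after 24 months are at the physician's discretion (Section 3.4.1.2). Both are right. They narrow the scope of the concern and of the fix without removing either.

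**Conclusion.** The concern holds. The required list covers 3 of the 4 electrolytes that Section 3.2.5i ties to serious reactions, and nothing else in the documents adds the fourth. This is an inconsistency in safety monitoring. It has no bearing on progression-free survival, the two-step decision rule or the stated error rates.

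Its clinical size cannot be stated, because the documents give no incidence of hypomagnesemia. The conclusion assumes that at least some sites would order exactly what the list and Table 3.4a require. Where a site already measures magnesium in its usual practice, the gap has no effect there. The change is worth making because the protocol itself asks for the monitoring and the cost is very low.

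**What to change.** Add magnesium to the mandatory blood chemistry list in Section 3.4.1.4.1. Table 3.4a needs no new row, since its chemistry row would then include magnesium at screening and at each scheduled 4-weekly sample. Coverage of the named electrolytes rises from 3 of 4 to 4 of 4.

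The change would not clearly govern the period after 24 months. If magnesium is wanted there too, Section 3.4.1.2 should say so.

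The cost is one further assay per panel (20 + 1 = 21 analytes) on blood already drawn. No extra visit, blood draw or statistical change is needed. The protocol amendment requires IRB approval in the usual way.
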